**The baseline assessments to be made at the research visit include:**

**Symptom questionnaire**

Parents of all patients will complete a written questionnaire to obtain details of symptom duration, onset and severity, including history of medications, allergies, family history. All parents will also be shown a validated video questionnaire to obtain objective confirmation of wheeze(31). Health related quality of life (HRQOL) for the child and family will be determined using the validated Child Health Questionnaire(32-34).

**Sample collection** – all parents will be asked for consent for the child to undertake FeNO measurement, have a blood sample taken, undergo sputum induction and have an oropharyngeal swab taken.

**1.** **Blood** will be taken for a peripheral eosinophil count, total IgE and specific IgE to common aero and food allergens.

**2.** **Sputum** induction will be performed using nebulised hypertonic saline (3.5%), chest physiotherapy and oropharyngeal suction using previously described techniques for preschool children. We have now established a protocol for sputum induction in preschool children with various airways diseases, including wheezing, and have shown the procedure can be performed safely and with up to 95% success. Sputum will be processed for bacterial culture and cytology.

**3.** **Lung function** will be performed using the multiple breath washout technique to obtain a measurement of lung clearance index (LCI) as previously described, and according to recent American Thoracic Society recommendations. This technique does not require voluntary manoeuvres and needs minimal patient cooperation and is therefore suited to preschool children. We have recently performed a pilot feasibility study in preschool children attending the outpatient clinic, and demonstrated only 27% were able to perform LCI, but if the index was reduced to gas clearance in half the time (LCI0.5), the success rate increased to 77%. Importantly, it has been shown that LCI measurements can be reliably shortened in children to improve the feasibility of obtaining data. We will therefore perform LCI and LCI0.5 in this study, and will be able to use the data for more formal assessments of feasibility in preschool children with wheeze. This has not been reported to date. Incentive spirometry using computer aided incentive devices will also be performed, but the success of this is anticipated to be lower than that for LCI.

**3.** **Exhaled nitric oxide** will be measured using the offline tidal breathing technique, with samples assessed using the NiOX chemiluminescence analyser. The recently published reference values for preschool children will be used to define elevated values.

**4. 5. Urine will be obtained and stored if parents consent to this.**

Formatted: Font: 12 pt

### **8.3 TREATMENT PROCEDURE**

The treatments to be used and each arm has been described in Section 6.1 above

### **8.4 SUBSEQUENT ASSESSMENTS**

Children will not routinely be brought back for follow-up during the 4 month intervention period.

Their compliance with the treatment prescribed will be monitored using electronic monitoring devices for the inhaled treatment, and by weekly telephone calls by the research nurse to remind the family of the importance of making sure the treatment is given daily for the period prescribed.

A symptoms diary will not be kept by the parents during the intervention period, but an automated text will be sent to the parents daily asking whether or not their child had any

symptoms of wheeze in the last 24 hours – the answer to the text will be a simple “yes” or “no” response.

**Immediate follow-up assessment:**

After the 4 month intervention period, all children will be asked to return for a follow-up visit during which the following assessments will be made:

**Symptoms** – using symptom questionnaire

**Health related quality of life** questionnaire

Number of unscheduled healthcare visits in the 4 month period (these will also have been recorded during the weekly telephone calls)

**Lung function** assessment (using multiple breath wash-out technique as described in Section 8.2 above)

**Exhaled nitric oxide** measurement (using the offline tidal breathing technique as described in Section 8.2 above)

**Sputum induction** – to assess inflammation and infection

Urine- for storage if parents consent

**Long-term follow-up assessments:**

After the first follow-up visit at 4 months, parents of children will be contacted at 6 months by phone call to assess symptoms, unscheduled healthcare visits, courses of steroids and medication. They will also be asked to attend annually for a follow-up visit when all of the above plus lung function, exhaled nitric oxide and sputum induction will be performed. Urine samples will also be collected and stored if parents consent. These assessments will continue until the end of the trial period, or until the child reaches the age of 6 years, whichever is sooner.

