**OUTCOME MEASURES:**

**Primary outcome** – number of unscheduled healthcare visits (UHCV) during the 4 month intervention period

**Secondary outcomes** – health related quality of life, number of hospital admissions, number of days of oral steroids during the 4 month intervention period, and up to 1 year later

**POPULATION:** Preschool children, aged 1-5 years attending out-patient clinic for recurrent wheezing

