## **3. STUDY DESIGN**

This is a single blind, randomised, controlled trial comparing management of moderate to severe preschool wheeze according to current clinical guidelines to management determined by inflammation and infection profile (pathological phenotype).

**Study duration:** The intervention phase of the study will last for 4 months, with follow-up immediately after the intervention period and 6 monthly thereafter until the end of the trial. The minimum follow-up is at the end of the 4 month intervention period, maximum follow-up will be for 3 years. During the 4 month intervention period, families will be contacted weekly by phone call for an update on unscheduled healthcare visits and symptoms.

**Type of subjects to be recruited:** All subjects will be aged between 1 and 5 years old. All subjects will have moderate to severe preschool wheeze, defined as  $\geq 2$  oral steroid bursts OR hospital admissions for acute wheeze in the last 12 months, with at least one oral steroid burst OR hospital admission in the last 6 months.

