### **Number of subjects:**

Based on published data for children with moderate preschool wheeze it is apparent that approximately five healthcare attendances occur per child per year. In the current study, we wish to reduce the proportion of healthcare contacts by at least one-third per year. In order to achieve this with 80% power, and accepting statistical significance at the 5% level, we require a minimum of 36 evaluable patients with moderate wheeze per group. Evaluable patients are those from whom at least a blood sample to assess inflammation and an oropharyngeal swab to determine infection can be obtained prior to randomisation.

A total of at least 72 children will therefore be recruited. However, this is the minimum number, and we aim to recruit 100 children (50 per group) if possible.

The number of subjects is not based on a precise power calculation as this is a proof of concept study to determine the feasibility of this approach, and to inform a future power calculation for a large multi-centre trial addressing the same question.

**3.1 Study Outcome Measures:** Primary outcome – number of unscheduled healthcare visits in the 4 month intervention period. Secondary outcomes – health related quality of life for the child and family, number of hospitalisations, days of oral steroids.

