#### **4.2 Inclusion criteria**

Age  $\geq$  1 years, <6 years  
Reported recurrent wheeze, needing at least 2 admissions +/- oral steroids in the last 12 months, at least one admission +/- oral steroids in the last 6 months

Past wheeze confirmed by a clinician

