## 5. RANDOMISATION AND ENROLMENT PROCEDURE

### 5.1 Randomisation practicalities

All randomisation and enrolment will occur during routine working hours – as all research visits will take place in the Biomedical Research Unit during the week between 9am and 5pm. Children will be recruited when they are clinically well, not during an acute attack.

We will use the Imperial INFORM database Unit to undertake randomisation

We wish to stratify randomisation according to sex and age, to achieve similar numbers of boys and girls in each group, and to have a similar average age for each group.

The age stratification will be as follows: >1-  $\leq$ 3 years and >3 -  $\leq$ 5 years

As wheezing in preschool children is a seasonal disorder (majority of symptoms and exacerbations occur between September – April each year), the baseline assessments and pre-randomisation visits will be arranged between late August – December each year, so that randomisation and intervention take place between September – January each year, to allow the 4 month intervention period to fall within the main season.

All patients will be given a study specific 24hrs emergency contact card immediately after being randomised. The card includes details of the study: Study title, patient trial number, CI/PI's contact details along with out of hours contact details in case of emergency.

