**8.5 LOSS TO FOLLOW-UP**

All attempts will be made to stay in touch with families, initially weekly phonecalls will be undertaken during the intervention period to stay in touch, and subsequently, even if they do not wish to attend the hospital for follow-up visits, information will be obtained by phone call about symptoms, medication and unscheduled healthcare visits. If a family cannot be contacted, the GP and local hospital will be contacted to determine any change of address.

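### Long-term assessments stop at the sixth birthday, so on a 16-month reading the oldest entrants cannot complete the 1-year extension of the secondary outcomes

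*Combined protocol and SAP*

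**What the plan says.** Four parts of the protocol bear on this.

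- **Stop rule.** Section 8.4, under the long-term follow-up heading: "These assessments will continue until the end of the trial period, or until the child reaches the age of 6 years, whichever is sooner".
- **Entry age.** Section 4.2 sets the limits as "1 years, <6 years" (the first with a greater-or-equal sign). The Study Summary describes the population as "Preschool children, aged 1-5 years attending out-patient clinic for recurrent wheezing", which can mean up to the fifth birthday or up to just under the sixth. Section 5.1 introduces the randomisation bands with "The age stratification will be as follows"; the upper band ends at 5 years.
- **Outcome window.** The Study Summary lists quality of life, hospital admissions and "number of days of oral steroids during the 4 month intervention period, and up to 1 year later". Section 3.1 gives the same outcomes with no 1-year window: "Secondary outcomes – health related quality of life for the child and family, number of hospitalisations, days of oral steroids".
- **Length of follow-up.** Section 3 says: "The minimum follow-up is at the end of the 4 month intervention period, maximum follow-up will be for 3 years".

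The visit at the end of the intervention (Section 8.4, immediate follow-up) is for all children and carries no age limit. Section 8.5 already accepts follow-up without attendance: "even if they do not wish to attend the hospital for follow-up visits, information will be obtained by phone call". Section 9 names a t-test or Mann-Whitney test for numerical data and Poisson regression for the primary endpoint. It does not say how unequal follow-up will be handled.

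**The concern.** The entry limit, the outcome window and the stop rule do not fit together for the oldest children. A secondary outcome is defined over a period in which the protocol itself ends the data collection for some of those enrolled, and the loss is fixed by age at entry.

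Two things are at stake. First, the 1-year results would lean towards the younger children. Age-stratified randomisation should keep the arms similar in this respect, but it does not bring back the missing follow-up. Secondly, a child observed for only part of the year may enter a comparison of totals as a low count, or be dropped, and Section 9 does not say which. For example, a child who enters at 5 years 5 months reaches 6 after 7 months, and so gives 3 of the 12 post-intervention months.

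**Working it through.** The protocol states no figure for the share of children who reach the 1-year point, so there is none to reproduce.

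**Inputs.** Stop at age 6 (Section 8.4); entry at 1 to <6 years (Section 4.2) or 1 to 5 years (Section 5.1 bands); window of 4 + 12 = 16 months from randomisation, or 12 months if the year is counted from randomisation (two readings of the Summary); planned size 72 to 100 children (Section 3). The trial's age distribution is not given and has to be assumed.

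**Cut-off age.** A child misses part of the window if entry age exceeds 6 − months/12.

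- 16 months: 6 − 16/12 = 4.667 years, that is 4 years 8 months.
- 12 months: 6 − 12/12 = 5 years.

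**Share incomplete, uniform ages on a to b:** (b − cut-off)/(b − a).

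| Entry ages | 16-month window | 12-month window |
|---|---|---|
| 1 to <6 | 1.333/5 = 26.7% | 1/5 = 20.0% |
| 1 to 5 | 0.333/4 = 8.3% | 0/4 = 0% |

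At 16 months, 26.7% is about 19 of 72 or 27 of 100 children; 8.3% is 6 of 72 or about 8 of 100.

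**Post-intervention person-time lost (16 months, uniform ages).** The fraction of the extension year lost rises linearly from 0 at entry age 4.667 to 1 at 5.667, and stays at 1 after that.

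- 1 to <6: (0.5 + 0.333)/5 = 16.7%. Those who contribute none of the extension: 0.333/5 = 6.7%.
- 1 to 5: (0.333²/2)/4 = 0.0556/4 = 1.4%.
- Upper band of Section 5.1 as written (over 3 to 5 years): 0.333/2 = 16.7% incomplete and 0.0556/2 = 2.8% of person-time lost.

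**Other assumed age mixes on 1 to <6, 16 months.**

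- Density falling linearly from age 1 to zero at 6: 1.333²/5² = 7.1%.
- Triangular with mode 3: 1.333²/(5 × 3) = 11.9%.
- Normal with SD 1.2, truncated to 1 to <6, centred at 2.5, 3, 3.5 and 4 (simulated): 3.8%, 8.1%, 15.3% and 25.5%.

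The only age figure nearby is a median of 3 years in Section 1.2. It describes national admissions and not this trial's entrants.

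**Second cause of truncation.** Section 8.4 also stops at the end of the trial, and Section 8.6 continues recruitment until funding ends in December 2018. If the trial ended on that date (an assumption), children randomised after about August 2017 (December 2018 minus 16 months) would miss part of the window at any age.

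**The case against.** The strongest reply is that variable follow-up is part of the design. Section 3 sets the minimum at the end of the intervention, the Summary's wording allows less than a full year, and Section 3.1 has no 1-year window at all. This is a proof-of-concept trial in preschool children, so ceasing to follow them at 6 may be deliberate. That stands as far as it goes, and it keeps the point at the level of a secondary extension. It does not remove it: if the window is fixed, the stop rule prevents some children from completing it; if it is variable, Section 9 needs a method for unequal observation time and has none.

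Several stronger readings are tempting, and the documents do not support them.

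- A reader might infer that about a quarter of children are lost. That is the result for uniform ages, the widest entry range and the longer window together. Nor is it a strict upper bound, since an older case mix could exceed it.
- A reader might run the upper age band to 6 and get 1.333/3 = 44% incomplete. Section 5.1 ends that band at 5.
- Because a child who enters after 5 years 8 months turns 6 during treatment, a reader might infer that intervention-period data are lost. The 4-month visit is for every child, and the stop rule stands under the long-term heading.
- A reader might take Section 9 to say that long-term totals will be compared as if windows were equal. It is silent on this, so low counts from short windows are a risk and not a stated plan.
- Nothing here shows bias between the arms.

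**Conclusion.** The conflict is real and confined to the post-intervention part of the secondary outcomes. If the window is 16 months from randomisation, no child who enters after about 4 years 8 months can complete admissions and oral-steroid days to one year after the intervention. The size cannot be fixed from the documents, because it turns on which age limit applies, when the year starts, and an unstated age distribution. Across the uniform-age readings it runs from 0% to 26.7%. The primary outcome and the 4-month secondary outcomes stand. The point should be corrected because a stated outcome cannot be fully collected as written and the remedy is cheap; it does not threaten the trial's main comparison.

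**What to change.** 1. **Section 8.4.** Exempt the 1-year outcomes that can be collected by phone (admissions and oral-steroid days) from the age-6 stop. Keep that stop only for the lung-function and sputum visits. The calls should record these two outcomes explicitly: the 6-month call now lists courses of steroids, while the Summary's outcome is days.
2. **Section 3.1 and the Summary.** State the same window in both, and say whether the year runs from the end of the intervention or from randomisation.
3. **Summary, Sections 4.2 and 5.1.** Reconcile the upper age limit, so that every eligible child falls in a randomisation band.
4. **Section 9.** Analyse the long-term counts as rates, with log observed person-time as an offset, instead of comparing raw totals. This is needed even after the first change, because the end of the trial can still shorten follow-up at any age. An offset corrects for the amount of time and not for its season. Section 5.1 describes wheeze as seasonal, so complete follow-up remains preferable to adjustment.

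The cost is protocol wording, one or two extra phone calls for each affected child, and slightly more analysis work. Section 8.5 already provides for phone-only information.

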**8.5 LOSS TO FOLLOW-UP**

All attempts will be made to stay in touch with families, initially weekly phonecalls will be undertaken during the intervention period to stay in touch, and subsequently, even if they do not wish to attend the hospital for follow-up visits, information will be obtained by phone call about symptoms, medication and unscheduled healthcare visits. If a family cannot be contacted, the GP and local hospital will be contacted to determine any change of address.

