### Hypothesis

Targeted treatment of preschool wheeze determined by airway inflammation and infection will result in better outcomes including fewer unscheduled healthcare visits, improved health related quality of life (HRQOL) for the child and family, and fewer days of oral steroid therapy compared to using current clinical guidelines.

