##### **4.1 Pre-randomisation Evaluations**

All participants will undergo an initial research / screening visit which will involve the following tests:

Full blood count and Vitamin D

Total serum IgE and RASTs to house dust mite, grass pollen, tree pollen, cat, dog, aspergillus, milk, egg, peanut

Assessment of lung function by incentive spirometry and lung clearance index (LCI) using the multiple breath washout technique  
Exhaled nitric oxide – using the offline tidal breathing technique  
Sputum induction using nebulised hypertonic saline  
Oro-pharyngeal swab  
Symptom questionnaire  
Health related quality of life questionnaire  
[Urine sample for cotinine levels \(and for storage if parents consent\)/salivary cotinine](#)

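### Families who miss the 4-month visit are offered a phone fallback that omits quality of life, so they have no HRQOL value for the 4-month comparison

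*Combined protocol and SAP*

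**What the plan says.** HRQOL has a clear standing in the plan. The Hypothesis in section 1.2 expects "improved health related quality of life (HRQOL) for the child and family", alongside fewer unscheduled visits and fewer days of oral steroids. Section 3.1 gives the secondary outcomes as "health related quality of life for the child and family, number of hospitalisations, days of oral steroids". The Outcome Measures entry of the Study Summary also lists HRQOL first among the secondary outcomes, and its time frame ends "number of days of oral steroids during the 4 month intervention period, and up to 1 year later".

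The instrument is named in section 8.2, under the symptom questionnaire: "Health related quality of life (HRQOL) for the child and family will be determined using the validated Child Health Questionnaire". The same paragraph opens with "Parents of all patients will complete a written questionnaire to obtain details of symptom duration, onset and severity". Section 4.1 lists HRQOL among the pre-randomisation evaluations.

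After treatment, HRQOL appears in section 8.4 under the immediate follow-up assessment, where "all children will be asked to return for a follow-up visit during which the following assessments will be made". For families who stay in contact but do not wish to come to the hospital, section 8.5 provides that "information will be obtained by phone call about symptoms, medication and unscheduled healthcare visits".

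**The concern.** Section 8.5 anticipates non-attendance and says what will be collected in that case. The primary outcome is covered twice, by the weekly calls and by the fallback call. HRQOL is covered by neither, although a questionnaire is one of the few items at the 4-month visit that need not depend on attendance. Lung function, exhaled nitric oxide and sputum induction do.

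Two things are at stake. First, the HRQOL comparison would rest on attenders alone. Section 4.4 commits to intention to treat, but section 9 gives no method for missing data, so the default is a complete-case t test or Mann-Whitney test. That loses precision. It could also bias the result if attendance is related to how the child has fared and differs by arm. Secondly, the trial is meant to inform a larger one, and HRQOL variance and completeness estimated from attenders would carry into that design.

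**Working it through.** **Step 1: does any contact collect HRQOL without attendance?** The scheduled contacts, side by side:

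| Contact | Where | HRQOL listed? | Attendance needed? |
|---|---|---|---|
| Baseline research visit | 4.1, 8.2 | Yes | Yes |
| Weekly calls during treatment | 3, 6.5, 8.4 | No (visits, symptoms, treatment reminders) | No |
| Daily text | 8.4 | No (yes/no on wheeze) | No |
| 4-month visit | 8.4, immediate follow-up | Yes | Yes |
| 6-month call | 8.4, long-term follow-up | No (symptoms, visits, steroid courses, medication) | No |
| Annual visit | 8.4, long-term follow-up | Not named | Yes |
| Fallback call | 8.5 | No (symptoms, medication, visits) | No |

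There are no routine visits during treatment (8.4). A family that declines the 4-month visit therefore has a baseline HRQOL value and no 4-month value. The annual visit might include HRQOL on a generous reading, but it falls at a different time, also needs attendance, and comes under the same fallback.

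**Step 2: could the questionnaire be done remotely?** Section 8.2 places the Child Health Questionnaire in the paragraph on what parents complete in writing, and the children are aged 1 to 5 years. Completion by parents is a strong inference, but the documents do not state it.

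**Step 3: loss of precision.** The plan has no figure to reproduce: it gives no power calculation for HRQOL and no non-attendance rate. Inputs:
- n = 36 per arm (the minimum) and 50 per arm (the aim), from section 3, Number of subjects.
- Two-sided 5% level and 80% power, the conventions the plan uses for its primary outcome.
- Assumed, not in the documents: a proportion q missing, equal in both arms, of 10, 20 or 30%.

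The number with HRQOL is m = n(1 - q) per arm. The detectable standardised difference d is the value at which a two-sample t test with 2m - 2 degrees of freedom has 80% power. The normal approximation is d ≈ (1.96 + 0.84) × √(2/m). For m = 36 it gives 2.80 × √(2/36) = 0.66, against 0.67 from the t distribution.

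| q | m (n = 36) | d, SD | m (n = 50) | d, SD |
|---|---|---|---|---|
| 0 | 36 | 0.67 | 50 | 0.57 |
| 10% | 32.4 | 0.71 | 45 | 0.60 |
| 20% | 28.8 | 0.75 | 40 | 0.63 |
| 30% | 25.2 | 0.81 | 35 | 0.68 |

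**Step 4: bias.** If non-attenders differ from attenders by δ SD in both arms, and the non-attendance proportions are p1 and p0, the complete-case arm difference is off by δ × (p1 - p0) in absolute size. The documents give neither δ nor p1 - p0, so no value follows. If non-attendance is equal in the arms and δ is the same in both, this bias is zero.

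**The case against.** The strongest reply is that section 8.5 says what will be obtained, not that nothing else may be. It does not forbid posting a questionnaire, and section 8.4 does not say that HRQOL can be completed only at the hospital. That is fair. A reader might infer a rule that discards HRQOL, but the text contains a gap and not such a rule. The gap still matters, because staff following the listed items would not collect it.

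A reader might also infer that the 4-month visit is the only post-treatment HRQOL measurement. The documents do not settle this: the Study Summary's time frame extends up to a year later, and the annual visit's reference back to earlier items can be read to include HRQOL. The point holds for the 4-month comparison and should be confined to it.

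A third tempting reading is that attendance will differ by arm and bias the result by a definite amount. For example, a 0.5 SD gap with 10% against 30% non-attendance gives 0.5 × 0.20 = 0.10 SD. Nothing in the documents supports those inputs. Both arms are asked back to the same visit, families will already have been asked to undergo the same procedures at baseline, and section 8.2 reports that sputum induction can be done safely and with high success. With 32.4 and 25.2 attenders, the standard error of the difference is √(1/32.4 + 1/25.2) = 0.27 SD, so even that scenario is small against sampling noise.

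The trial is also a proof of concept with no precise power calculation, and at 50 per arm with 30% missing it would detect about what 36 complete per arm would (0.68 against 0.67 SD). This limits the importance of the point but does not remove it.

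Finally, the complete-case default owes as much to section 9, which has no missing-data method, as to section 8.5. The fallback list also fails to name oral steroid days and hospital admissions, although admissions may be caught under unscheduled visits.

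**Conclusion.** The omission is real. As written, children whose families do not attend at 4 months have no HRQOL value for the 4-month comparison, while their primary outcome is still collected. The consequence is a loss of precision: under an assumed 10 to 30% missing, the detectable difference rises from 0.67 to 0.71-0.81 SD at 36 per arm, or from 0.57 to 0.60-0.68 SD at 50 per arm. These figures assume equal loss in both arms and a t-test comparison. Bias from selective attendance is possible but cannot be sized, and the documents do not show that it is likely. That the questionnaire can be completed away from the hospital rests on the inference that parents fill it in. The point concerns a secondary outcome only and does not touch the primary analysis. It is a cheap improvement.

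**What to change.** Add to section 8.5 that, for any family not attending the 4-month visit, the HRQOL questionnaire will be obtained by post, online or phone within a fixed window around month 4. Use the same self-completed form where possible, to limit differences between modes. Record the mode for every questionnaire. Include all returned questionnaires in the 4-month comparison, and report a sensitivity analysis restricted to forms completed at the visit.

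The plan should acknowledge that recording mode, or restricting to one mode, does not remove mode bias if mode differs by arm, because mode is then tied to attendance after randomisation. While section 8.5 is open, check whether its list should also name the other secondary outcomes.

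The cost is a short addition to the text, some postage or a longer call, and mixed modes of administration. The change uses contact that section 8.5 already promises.
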